### 8.3. Variables

The operational definitions will be included and detailed in the statistical analysis plan (SAP).

Variable	Role	Data Source(s)	Operational Definition
Core			
Study Site ID	Baseline	GloBE-Reg data base	Assessed at baseline
Demographics			
Date of birth	Baseline demographic	GloBE-Reg data base	Categorical month, day, year
Participant follow-up status	exposure	GloBE-Reg data base	Categorical Patient active, inactive, care suspended, care

			terminated, deceased, unknown
Date of death	outcome	GloBE-Reg data base	Categorical Month, day, year
Primary cause of death	outcome	GloBE-Reg data base	Categorical: See SAP
Sex at birth	Baseline characteristic	GloBE-Reg data base	Categorical male, female, other, unknown
Current gender	Baseline characteristic	GloBE-Reg data base	Categorical Male, female, non-binary, other, asked but unknown, unknown, same as sex at birth
Country at birth	Baseline demographic	GloBE-Reg data base	Categorical Select from any country in the world
Country of usual residence	Baseline demographic	GloBE-Reg data base	Categorical Select from any country in the world
Other			
Consent for PRO collection	Baseline	GloBE-Reg database	Categorical Yes, no, unknown
Participation in other registries (PROGRES 1.0)	Baseline demographic	GloBE-Reg data base	Categorical Yes, no, unknown
Name of registries (PROGRES 1.0 only)	Baseline demographic	GloBE-Reg data base	Free text box
Registry participant ID(s) (PROGRES 1.0 only)	Baseline demographic	GloBE-Reg data base	Free text box

090177e1a57a0182\Approved\Approved On: 16-Feb-2026 13:43 (GMT)

Treatments			
Drug group and sub-group	exposure	GloBE-Reg data base	Categorical drug
Commercial name of drug used	Treatment characteristic	GloBE-Reg data base	Categorical LAGH,dGH, Somatrogon, Genotropin
Drug Indication			
Drug indication type	Treatment characteristic	GloBE-Reg data base	Categorical
Drug indication:	Treatment characteristic	GloBE-Reg data base	Categorical  Drop down menu – select from indication options listed  Drug indication:  - Chronic Kidney Disease - Growth Hormone Deficiency (GHD)-type- Idiopathic short stature - Noonan syndrome - Prader Willi Syndrome - Skeletal Dysplasia – type - Small for Gestational Age (SGA) - type - Turner Syndrome - Other Disorder - type
hGH exposure			
visit date	exposure	GloBE-Reg data base	Categorical day, month, year

090177e1a57a0182\Approved\Approved On: 16-Feb-2026 13:43 (GMT)

assessment date	exposure	GloBE-Reg data base	Categorical day, month, year
start date of first rhGH therapy	exposure	GloBE-Reg data base	Categorical day, month, year
start date of current rhGH therapy	exposure	GloBE-Reg data base	Categorical day, month, year
Total weekly dose	exposure	GloBE-Reg data base	numerical variable numerical input (1-100)
change in dose since last visit	exposure	GloBE-Reg data base	Categorical yes, no, unknown
Reason for change	exposure	GloBE-Reg data base	Categorical drop down menu or free text – dose adjustment for size, to optimise growth, low IGF-1, high IGF-1, adverse events, other (free text)
Reported missed doses in an average month	exposure	GloBE-Reg data base	Categorical drop down menu – unknown, 1, 2, 3, 4 or 5
Reported missed doses in an average week	exposure	GloBE-Reg data base	Categorical drop down menu – unknown, 1, 2, 3, 4, 5, 6, 7
Therapy stopped	exposure	GloBE-Reg data base	Categorical drop down menu – unknown, not applicable, yes, no

090177e1a57a0182\Approved\Approved On: 16-Feb-2026 13:43 (GMT)

Date of therapy stop	exposure	GloBE-Reg data base	Categorical day, month, year
Reason for therapy stop	exposure	GloBE-Reg data base	Categorical drop down menu – not applicable, unknown, patient choice, poor efficacy, adverse events, final height achieved, other
Reinitiation of rhGH after final adult height	exposure	GloBE-Reg data base	Categorical drop down menu – unknown, not applicable,
Diagnosis			
Visit date	Treatment characteristic	GloBE-Reg database	Categorical Day-month-year
Date of assessment	Treatment characteristic	GloBE-Reg database	Day-month-year
Primary condition			
Primary condition:	Baseline clinical characteristic	GloBE-Reg database	Categorical Drop down menu - Chronic Kidney Disease - type GHD - Non-specific – type Acquired - CNS infection - Extracranial tumor - Intracranial tumor - Granulomatous disease - Other - Radiation therapy - Trauma - Vascular anomaly Congenital

090177e1a57a0182\Approved\Approved On: 16-Feb-2026 13:43 (GMT)

090177e1a57a0182\Approved\Approved On: 16-Feb-2026 13:43 (GMT)

			
 
- Genetic
 
- Idiopathic
 
- Other
 
- Prenatal infection
 
- Structural malformation
 
- Syndromic
 
 
Idiopathic short stature
 
Noonan Syndrome
 
Prader-Willi Syndrome and Prader-Willi like syndrome
 
Skeletal dysplasia
 
Achondroplasia
 
Hypochondroplasia
 
SHOX gene defect
 
Other skeletal dysplasia
 
Small for Gestational Age (SGA)
 
Silver-Russell Syndrome
 
IGF-I deficiency
 
IGF-I resistance
 
Prenatal infection
 
Drugs, alcohol or smoking related
 
Idiopathic
 
Turner Syndrome
 
Precocious puberty
 
Other disorder

--	--	--	--

Clinical Characteristics			
History of birth	Baseline characteristic	Globe Reg database	Categorical
Gestational age			Drop down menu: select unknown or week between 23-43
Delivery mode			Drop down menu: unknown, spontaneous vaginal delivery, forceps delivery, ventouse delivery, elective cesarean section, emergency cesarean section, other (text input)
Birth weight			Not known or whole number input (grams)
Relevant family history	Baseline characteristic	Globe Reg database	Categorical
Paternal height			Not known or whole number input (cm)
Maternal height			Not known or whole number input (cm)
Mid parental height			Calculated from paternal and maternal height (cm)
Puberty	Clinical characteristic	Globe Reg database	Categorical
Date			Day, month, year
Age at assessment			Calculated from date of birth
Genitalia (Tanner stage)			Drop down: unknown, not applicable, 1, 2, 3, 4, 5
Right testicular volume (mL)			Drop down: unknown, 1, 2, 3, 4, 5, 6, 7, 8, 9, 10, 11, 12, 13, 14, 15, more than 15 mL
Left testicular volume (mL)			Drop down: unknown, 1, 2, 3, 4, 5, 6, 7, 8, 9, 10, 11, 12, 13, 14, 15, more than 15 mL
Breast (Tanner stage)			Drop down: unknown, not applicable, 1, 2, 3, 4, 5

090177e1a57a0182\Approved\Approved On: 16-Feb-2026 13:43 (GMT)

Pubic hair (Tanner stage)			Drop down: unknown, not applicable, 1, 2, 3, 4, 5
Menarche attained (only for female patients)			Drop down: unknown, not applicable, yes, no
Menarche attained only for female patients (date)			Day, month, year
Auxological measures			
Age	Clinical characteristic	Globe-Reg Database	Automatic calculation from DOB
Height (primary effectiveness)	Baseline Clinical characteristic/outcome	Globe-Reg database	Numerical input
Weight	Baseline clinical characteristic/ outcome	GloBE-Reg database	Numerical input
BMI (primary effectiveness)	Baseline clinical characteristic/outcome	GloBE-Reg database	Automatic calculation from height and weight
Bone age (primary effectiveness)	Baseline clinical characteristic/outcome	GloBE-REg database	Categorical Drop down menu: unknown, not performed, performed
Bone age date performed	Baseline clinical characteristic/outcome	GloBE-REg database	Day, month, year
Bone age method	Baseline clinical characteristic/outcome	GloBE-REg database	Drop down: unknown, not applicable, Greulich-Pyle (GP), Tanner Whitehouse 2, Tanner Whitehouse 3, Radius-ulna-short bone, other
Value	Baseline clinical characteristic/outcome	GloBE-REg database	Text box
Further details	Baseline clinical characteristic/outcome	GloBE-REg database	Text box

090177e1a57a0182\Approved\Approved On: 16-Feb-2026 13:43 (GMT)

Comorbidities/ Medical history			
Other health conditions	Baseline clinical characteristics	GloBE-Reg database	Categorical  Drop down: unknown, not applicable, yes, no, text input
Date of assessment	Baseline characteristic	GloBE-Reg database	Day-month-year
Other health conditions:	Baseline characteristic	Globe-Reg database	Categorical
Neoplasia or cranial tumor	Baseline characteristic	Globe-Reg database	Unknown, Yes, no, text box
Cranial or total body irradiation	Baseline characteristic	Globe-Reg database	Unknown, Yes, no, text box
Chemotherapy	Baseline characteristic	Globe-Reg database	Unknown, Yes, no, text box
Traumatic brain injury	Baseline characteristic	Globe-Reg database	Unknown, Yes, no, text box
Pituitary or cranial surgery	Baseline characteristic	Globe-Reg database	Unknown, Yes, no, text box
Concomitant medication			
Assessment date	Clinical characteristic/exposure	GloBE-Reg database	Categorical  Day, month, year
Thyroid hormone - Dose - Date started - Date stopped  Glucocorticoid - Total daily dose	Clinical characteristics/exposure	GloBE-Reg database	Categorical  Medication: yes, no, unknown  Dose: numerical input

090177e1a57a0182\Approved\Approved On: 16-Feb-2026 13:43 (GMT)


 
- Date started
 
- Date stopped
 
 
Oestrogen
 
 
- Type/route/dose
 
- Date started
 
- Date stopped
 
 
Gonadotrophins
 
 
- Type/route/dose
 
- Date started
 
- Date stopped
 
 
Testosterone
 
 
- Type/route/dose
 
- Date started
 
- Date stopped
 
 
DDAVP
 
 
- Type/route/dose
 
- Date started
 
- Date stopped
 
 
Other medication(s)
			
Date started/date stopped: day, month, year
 
Prior medications will be defined as medications that are utilized prior to baseline. Concomitant medications will be defined as medications that are utilized on or after baseline.

Laboratory measures
			

IGF-I (primary effectiveness)
 
 
- Date performed
 
-Time performed to the nearest hour
 
-Date of last rhGH injection
 
-Time of last injection to the nearest hour
 
- Result
 
- Value and units
 
- Assay
 
- Other details (if available)
 
	
Baseline clinical characteristic/outcome
	
GloBE-Reg database
	
Categorical or numerical value
 
drop down menu – unknown, not performed, performed
 
see SAP

GH stimulation test(s)
 
 
- Date performed
 
- Type
 
- GH peak level
 
	
Baseline Clinical characteristic/outcome
	
GloBE-Reg database
	
Categorical or numerical value

090177e1a57a0182\Approved\Approved On: 16-Feb-2026 13:43 (GMT)

- GH peak value and units			drop down menu – unknown, not performed, performed see SAP
TSH - Date performed - Result - Value and units	Clinical characteristic/outcome	Globe-Reg database	Categorical or numerical value  drop down menu – unknown, not performed, performed see SAP
Free T4 - Date performed - Result - Value and units	Clinical characteristic/outcome	Globe-Reg database	Categorical or numerical value  drop down menu – unknown, not performed, performed see SAP
HbA1c - Date performed - Result - Value and units	Clinical characteristic/outcome	Globe-Reg database	Categorical or numerical value  drop down menu – unknown, not performed, performed see SAP
Imaging			
MRI pituitary	Clinical characteristic/outcome	Globe-Reg database	Categorical  drop down menu – unknown, not performed, performed
Date performed	Clinical characteristic/outcome	Globe-Reg database	Categorical  Day, month, year
Results	Clinical characteristic/outcome	Globe-Reg database	See SAP
Further details	Clinical characteristic/outcome	Globe-Reg database	Text input

090177e1a57a0182\Approved\Approved On: 16-Feb-2026 13:43 (GMT)

Adverse events and exposure scenarios			
Adverse events	Outcome	GloBE-Reg database	Categorical
Date of assessment	Outcome		Categorical Day, month, year
Seriousness	Outcome		Categorical See SAP
Causality	Outcome		Categorical Drop down menu – probable, possible, unlikely
Further details	Outcome		Categorical Text box input
Blood and Lymphatics	Outcome		Categorical Tick boxes: - Anaemia  - Eosinophilia - Leukaemia - Peripheral Oedema - Other
Endocrine and metabolic	Outcome		Categorical Tick boxes:  - Adrenal Insufficiency - Gynaecomastia - Hyperglycaemia - Hypothyroidism - Type 2 Diabetes Mellitus (T2DM) - Other
ENT	Outcome		Categorical

090177e1a57a0182\Approved\Approved On: 16-Feb-2026 13:43 (GMT)

			Tick boxes: -Epistaxis -Nasopharyngitis -Other
Eyes	Outcome		Categorical Tick boxes: -Conjunctivitis -Other
Gastrointestinal (GI)	Outcome		Categorical Tick boxes: -Nausea -Pancreatitis -Vomiting -Other
Immune system	Outcome		Categorical Tick boxes: -Anaphylaxis -Angioedema -Anti-GH Antibodies -Immunogenicity -Other
Injection site reaction **	Outcome		Categorical Tick boxes: -Bruising -Erythema -Haematoma -Lipoatrophy -Localised Pain -Swelling -Other
Musculoskeletal	Outcome		Categorical

090177e1a57a0182\Approved\Approved On: 16-Feb-2026 13:43 (GMT)

090177e1a57a0182\Approved\Approved On: 16-Feb-2026 13:43 (GMT)

			Tick boxes: -Arthralgia -Arthritis -Myalgia -Myositis -Scoliosis -Slipped upper femoral epiphyses -Other
Neoplasm *	Outcome		Categorical Tick boxes: -Primary neoplasm -Secondary Neoplasm -Other
Nervous system	Outcome		Categorical Tick boxes: -Ataxia -Dizziness -Headache -Intracranial Hypertension -Paresthesia -Other
Renal	Outcome		Categorical Tick boxes: -Hematuria -Other
Skin	Outcome		Categorical Tick boxes: Rash/urticaria/pruritus -Other

Exposure scenarios: Medication error	outcome	GloBE-Reg database	Categorical  - Visit date - Date of assessment - Type of medication error (accidental/intentional) - Classification (wrong drug/route/frequency/dose/other) - Date when it occurred - Date when it was reported to physician - Report to authorities details - Adverse events associated with medication error - Other details  See SAP
---	---------	--------------------	---

Baseline date is the initial visit date on the Reported Outcomes eCRF form.

The potential covariates and confounders that will be considered for the models in addition to treatment (Genotropin and Ngenla) are the following baseline variables, classified into different categories:

**Table 8-3 Model Covariates**

Priority Order*	Model Covariates	Propensity Score Model Covariates - Categories
7	Geographic region	Region (Europe, NA, Japan and RoW)
1	Demographics	Age (in years), Sex
2	Clinical characteristics	Height, Weight
3	Naive to GH status	Naïve to GH/Non-Naïve to GH
4	Peak GH levels	≤3 ng/mL, >3 ng/mL to ≤7 ng/mL, >7 ng/mL to 10 ng/mL, >10 ng/mL
5	Duration of GH (time from first rhGH therapy)	
6	Time since start of the study (in months)	

090177e1a57a0182\Approved\Approved On: 16-Feb-2026 13:43 (GMT)

\*This priority order will be used to remove the least priority variables in case of non-convergence issues for the model. Additional variables and its priority order can be decided during the analysis. Relevant patient/disease characteristics, including baseline value of the variable to be analyzed, will also be included whenever applicable.

#### 8.4. Data Sources

The study will obtain existing data collected in the GloBE-Reg registry. GloBE-Reg is an international, non-interventional registry of bone and endocrine agents, conducted by the project team based at the Office for Rare Conditions at the University of Glasgow, Glasgow, Scotland, United Kingdom. GloBE-Reg is approved by the National Research Ethics Service and Information Governance Authority in the UK.

The registry collects real-world data on both efficacy and safety and allows for sub-studies that can be of interest to any of its stakeholders. The GloBE-Reg steering committee identified an expert working group to develop a minimum data set for the registry. The minimum data set comprises items agreed upon by the expert working group and deemed by consensus to be easily measured in a routine clinical setting across the world to monitor the safety and effectiveness of hGH, both daily and long acting, in children with GHD. To date, GloBE-Reg has collected de-identified, patient-level data from an international cohort of over 3500 participants from across 32 centers in 20 countries. The collected data is comprised of demographics, clinical characteristics, birth and medical history, diagnosis of growth hormone deficiency, therapy, including prior and current GH treatment, concomitant medications, laboratory results, clinician reported outcomes and adverse events.

The registry is a web-based interface linked to a secure database at the University of Glasgow, which is managed and reviewed by the university Central IT Services in compliance with the UK Data Protection Act (2018) and General Data Protection Regulation (GDPR 2016/679). Reporters are healthcare professionals at medical institutions around the world who apply for clinical contributor role-based access accounts for their center. Once access to the registry is obtained, clinicians obtain local approvals to enroll eligible participants at their center, obtain and store each participant informed consent form and can then add routinely collected clinical information. All data are pseudonymized and when the core mandatory modules are entered into the registry and saved, a registry ID is provided. This unique patient identifier is used across all visits, enabling longitudinal follow-up of patients.

Data can also be uploaded using bulk transfer method available in the registry, after the above requirements are met.

Data entered in the GloBE-Reg database will be formally assessed for quality on an annual basis. Ten percent of cases (or a minimum of 1) included from each center shall be eligible for a remote quality assurance (QA), with cases selected using a randomization tool. For the selected cases, the center lead clinician is invited to submit evidence through the QA platform that is built into the registry, and the GloBE-Reg team arranges a meeting to discuss the process in detail.

In addition, the useability of the platform for data entry is checked through biannual user surveys. Limited internal validation protocols and required mandatory completion checks are performed. During subsequent processing and analysis, outliers and missing values are identified and reviewed.

## 8.5. Study Size

The study is descriptive in nature without any *a priori* hypothesis testing; therefore, a formal sample size estimate is not required. All eligible participants treated will be included. It is expected that at least 2000 Genotropin (somatropin) treated and 700 Ngenla (somatrogon) treated participants will be included in the final analysis.

## 8.6. Data Management

All data for this study will be collected through the routine data collection practices of the GloBE-Reg registry. Investigators in each country will independently generate the data needed for the registry. The investigators will check the data for consistency in terms of range of values, units of measurement, and relevance of clinical information.

The registry is a web-based interface linked to a secure database at the University of Glasgow, and investigators at centers around the world add pseudonymized, routinely collected clinical data on patients who provide consent to participate in the registry. Data contained in other databases and registries can also be uploaded using a bulk transfer method, which avoids manual double entry through bulk upload of core and longitudinal data.

All participant data is stored by GloBE-Reg on a secure physical server at the University of Glasgow, which is managed and reviewed by Central IT Services. Additional details can be found in University of Glasgow's Data Protection Impact Assessment (DPIA) document (Annex 1).

Data for participants treated with Ngenla (somatrogon) and Genotropin (somatropin) will be provided to Pfizer only after centers provide consent to share their data. Data transferred to Pfizer will be in CSV format every 6 months using CONFORM 4.0.10 or later via secure file transfer protocol and stored internally on a secured dedicated server. The data will be converted to SAS format for analysis and reporting and will be processed by Pfizer to create analytical variables and datasets for all analyses specified in the study protocol. All study data will exist as structured data by the start of the study. The data analysis and results generation will strictly follow the approved SAP. If for any reason any statistical method needs to be carried out differently than described in the SAP, an amendment to the SAP with required documentation and new approval will be done. All computations and generation of Tables, Listings and Data for figures will be performed using SAS Version 9.4 or higher.

## 8.7 Data Analysis

Data on the subset of participants in the GloBE-Reg registry who are treated with Ngenla (somatrogon) or Genotropin (somatropin) will be obtained and analyzed. The data will be converted to SAS format for analysis and reporting and will be processed by Pfizer to create analytical variables and datasets for all analysis specified in the study protocol. All study data will exist as structured data by the start of the study. Data obtained from GloBE-Reg will not undergo any additional cleaning or error checks, and there will be no imputation of missing data. All data received from GloBE-Reg will be analyzed. The study is descriptive in nature without *a priori* hypothesis testing.

090177e1a57a0182\Approved\Approved On: 16-Feb-2026 13:43 (GMT)

Analysis of Primary Endpoint:

The primary analysis is to compare effectiveness of Ngenla (Somatrogon) and Genotropin (Somatropin) during the course of routine clinical care. The primary endpoints are height, bone age, body mass index (BMI) and insulin-like-growth factor-I (IGF-I) levels.

The primary effectiveness outcomes for height (Annual HV, HVSDS, change in height SDS) will also be presented by subgroups. The following subgroups will be defined, as categorized at baseline.

- Age group (0 to 2, 3 to 8, 9 to 18, ≥19 years)
- Sex (Male, Female)
- Naïve/Non-naïve to rhGH therapy.
- Puberty Status (Yes, No)
- Medical co-morbidities (Yes, No)
- Initial disease/treatment indications (Yes, No)
- Peak growth hormone (GH) levels ≤3 ng/mL, >3 ng/mL to ≤7 ng/mL, >7 ng/mL to 10 ng/mL, > 10 ng/mL
- Primary Condition/Diagnosis (CKD, GHD (Non-specific, Acquired, Congenital, Idiopathic), Idiopathic Short Stature, Noonan Syndrome, Prader-Willi Syndrome, SGA, *etc.*)
- Study region (Europe, Japan, North America, Rest of the World)

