## 6. RATIONALE AND BACKGROUND

Human growth hormone (hGH) is a 191-amino-acid pituitary protein that stimulates production and release of insulin-like growth factor-I (IGF-I). Growth hormone (GH) and IGF-I are the primary mediators of the promotion of growth in children and play a role in the regulation of body composition and metabolism in children and adults. These factors are regulated through complex feedback mechanisms involving hGH, and IGF-I (1, 2). Growth hormone deficiency (GHD) results in inadequate circulating IGF-I level and is manifested as abnormal growth (linear growth) in children (3, 4). Childhood GHD can be congenital, acquired, or idiopathic. The underlying causes for congenital GHD may include genetic abnormalities and pituitary dysfunction due to abnormal neurodevelopment *in utero* of certain brain regions. Acquired GHD may result from brain tumors in the hypothalamic region, traumatic brain injury, infiltrative disease, cranial irradiation, and surgical intervention. Generally, the origin of idiopathic GHD is complex and multifactorial, and thus is not fully understood (5).

Data on the incidence and prevalence of GHD are limited. A population-based (nationwide) study in Denmark reported average incidence rate (IR) of 2.58 males, and 1.7 females per 100,000 for childhood onset of GHD (6). For prevalence, rates were comparable in studies conducted in Belgium and the United States (US). The Belgian study, conducted between 1986 and 2001, estimated the prevalence of childhood GHD to be 1/5600. The origin of GHD was idiopathic in 41% of the participants, congenital in 20%, acquired in 7% and 4% of the participants had a defined syndrome accompanying GHD; there was male predominance in all the categories (7). In the US study, the prevalence of GHD in the 1990's was at least 1:3480, with male predominance (8). The incidence has remained fairly constant over the last 2 decades. Most morbidity in children with GHD relates to short stature and abnormal metabolism. The inability to reach normal height can lead to early onset of severe psychosocial problems, along with accompanying problems such as delayed puberty and deficits in facial, dental and (in males) genital development. Lastly, GHD that persists into adulthood is associated with an increased risk of cardiovascular morbidity and mortality (3).

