### 8.2. Setting

The source population for this study will be the subset of patients contributing data to the GloBE-Reg registry who are treated with either long acting Ngenla (somatrogon) or daily hGH Genotropin (somatropin) at the discretion of the prescribing physician. This population is thought to be a representative sample of children treated with Ngenla (somatrogon) and Genotropin (somatropin) across the world. Data will be included from eligible participants of any age who meet the study criteria and who receive care at centers enrolled in GloBE-Reg that have agreed to share their data with Pfizer during the data collection period. The registry is growing and additional centers around the world are expected to be included over the course of the study period.

The data collection period is from September 30, 2025 to August 31, 2035. No sampling will be performed. Participants can be located anywhere in the world and will be followed up to 10 years until the end of the study or one of the following occurs: withdrawal of consent, discontinuation of

either Ngenla (somatrogon) or Genotropin (somatropin), discontinuation from the GloBE-Reg registry, lost to follow up or death.

The treating physician will follow patients treated with Genotropin (somatropin) or Ngenla (somatrogon) as per routine clinical practice and will collect and enter relevant patient data as part of the defined minimum data set collected by the GloBE-Reg registry.

During the study, duration of treatment exposed will be defined as:

Genotropin/Ngenla: (last dose date – baseline date + 1)/365.25,

where baseline date is the initial visit date on the Reported Outcomes eCRF form.

The data collected via GloBE-Reg will be de-identified and sent to Pfizer for analysis. Pfizer will analyze the data to evaluate treatment effectiveness, safety, adherence and compliance.

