**Table 8-7 Overview of Effectiveness Analysis**

Outcome	Primary/Secondary	Statistical Method 1	Statistical Method 2	Statistical Method 3
Annual HV	Primary	MMRM, 95% CI	MMRM + IPTW, 95% CI	Descriptive stats
Height standard deviation score (SDS) and change in height SDS	Primary	MMRM, 95% CI	MMRM + IPTW, 95% CI	Descriptive stats
HVSDS	Primary	MMRM, 95% CI	MMRM + IPTW, 95% CI	Descriptive stats
Change in annual BMI	Primary	MMRM, 95% CI	MMRM + IPTW, 95% CI	Descriptive stats
Change in annual BMI SDS	Primary	MMRM, 95% CI	MMRM + IPTW, 95% CI	Descriptive stats
Change in Bone age	Primary	MMRM, 95% CI	MMRM + IPTW, 95% CI	Descriptive stats
Change in IGF	Primary	MMRM, 95% CI	MMRM + IPTW, 95% CI	Descriptive stats
Change in IGF-I SDS	Primary	MMRM, 95% CI	MMRM + IPTW, 95% CI	Descriptive stats

090177e1a57a0182\Approved\Approved On: 16-Feb-2026 13:43 (GMT)

[1] Continuous variables will be summarized using descriptive statistics which will include the number of patients with data to be summarized (n), mean, standard deviation (SD), median, first and third quartiles (Q1, Q3), minimum, maximum, and the number of missing observations. Descriptive statistics for categorical/qualitative variables will be presented with number of patients (count) and percentage and this will be presented in the format 'n (%)'.

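### Annual HV and HVSDS are primary outcomes at every age: they carry no usable information at 19 years or older, and at 9 to 18 HVSDS can reflect puberty timing as well as drug effect

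*Protocol*

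**What the plan says.** Table 8-7 (Overview of Effectiveness Analysis) lists Annual HV, height SDS with its change, and HVSDS as separate primary outcomes. The HVSDS row reads "HVSDS Primary MMRM, 95% CI MMRM + IPTW, 95% CI Descriptive stats". It carries no limit by age, puberty, bone age or remaining growth.

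Section 8.2 sets no age bounds: "Data will be included from eligible participants of any age who meet the study criteria". Section 8.7 adds that everything received from the registry will be analysed.

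Section 8.7 then states: "The primary effectiveness outcomes for height (Annual HV, HVSDS, change in height SDS) will also be presented by subgroups". The age bands are "Age group (0 to 2, 3 to 8, 9 to 18, ≥19 years", and puberty is handled as "Puberty Status (Yes, No". On timing it says: "The following subgroups will be defined, as categorized at baseline". Follow-up under Section 8.2 can last 10 years.

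The demographic entry in Table 8-3 is "Age (in years), Sex". Puberty status, Tanner stage and bone age are not listed, although Section 8.3 shows that dated Tanner stages, testicular volume and menarche are collected.

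Section 6 names "accompanying problems such as delayed puberty" among the consequences of the condition and says that treatment usually runs to adult height or epiphyseal closure. Section 8.3 has a field for restarting therapy after final adult height.

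**The concern.** There are two separate problems.

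**Age 19 or older.** Growth has normally ended. A velocity SDS divides a near-zero velocity, plus measurement error, by a reference SD that is itself near zero or does not exist. Annual HV can still be calculated but says nothing about drug effect. Because Table 8-7 sets no limit, these near-zero velocities also enter the overall HV model beside those of growing children.

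**Age 9 to 18.** If HVSDS is referenced to chronological age, the reference assumes average puberty timing. A late-maturing child scores too low while peers are in their growth spurt and too high when the child's own spurt comes later, whichever drug is given. Classifying puberty at baseline does not follow a child who enters puberty during follow-up. The distortion changes sign with age, so an age term would not readily absorb it.

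At stake is whether two of the primary outcomes can be read as drug effects in these age bands, and whether the pooled drug difference picks up differences in age or maturity between the arms.

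**Working it through.** The protocol gives no sample-size calculation, HVSDS reference, SD or age mix, so there is no stated figure to reproduce. What follows is illustration. Every reference value is an assumption.

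**Inputs from the protocol:** expected 2000 Genotropin and 700 Ngenla participants (Section 8.5); pivotal-trial HV of 10.10 and 9.78 cm/year (Section 6), a difference of 0.32 cm/year.

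**1. Individual scores**, HVSDS = (HV - reference mean) / reference SD:

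| Case | HV (cm/y) | Reference mean | Reference SD | HVSDS |
|---|---|---|---|---|
| Prepubertal boy, about 14 | 5 to 6 | 8 to 9.5 | 1.0 to 1.5 | (5 - 9.5)/1.0 = -4.5 to (6 - 8)/1.5 = -1.3 |
| Late-maturing boy, 16 to 17 | 6 to 8 | 1 to 3 | 0.8 to 1.3 | (6 - 3)/1.3 = +2.3 to (8 - 1)/0.8 = +8.8 |
| Adult, true velocity 0, measurement error 0.5 | 0.5 | 0 | 0.1 to 0.3 | 0.5/0.3 = +1.7 to 0.5/0.1 = +5.0; undefined at SD 0 |

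**2. Effect on an arm mean** = share affected x artefact, taking artefacts of -3 or +4 SDS:

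| Share affected | Shift at -3 | Shift at +4 |
|---|---|---|
| 5% | -0.15 | +0.20 |
| 10% | -0.30 | +0.40 |
| 20% | -0.60 | +0.80 |
| 40% | -1.2 | +1.6 |

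The same products give the bias in the drug difference when the share is read as the between-arm difference in affected participants. A 10-point imbalance gives -0.3 to +0.4 SDS. With equal shares and equal artefacts the shifts cancel.

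**3. Sampling error for comparison.** The half-width of a simple two-arm 95% CI is 1.96 x SD x sqrt(1/2000 + 1/700). The square root is 0.0439, giving 0.13, 0.17 and 0.26 SDS for assumed SDs of 1.5, 2 and 3. A 10-point imbalance therefore exceeds the half-width at each of these SDs; a 5-point imbalance (-0.15 or +0.20) exceeds it only towards the smaller SDs.

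**4. Adults in the pooled HV model.** If non-growing participants contribute 0 and growing ones contribute 9.78 cm/year, an unadjusted between-arm difference d in the share of non-growing participants shifts the HV difference by 9.78 x d. To match 0.32 cm/year, d = 0.32/9.78 = 3.3 percentage points. If growing participants average half that velocity (4.89), d = 0.32/4.89 = 6.5 points. Adjustment for age or baseline value would reduce this by an amount that cannot be worked out from the protocol.

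**The case against.** The strongest reply is that Section 8.3 leaves operational definitions to the SAP, which is not shown. The HVSDS reference and its evaluable age range are ordinary SAP content. This stands for the reference, and it is why the 9 to 18 argument is conditional. It does not answer the 19-or-older point: the protocol itself orders HV and HVSDS for that band, and Section 8.7 says that major changes to primary endpoint definitions or analyses would be reflected in a protocol amendment.

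The protocol also has mitigations. Results are split by age, sex and baseline puberty; age and sex are listed model covariates; further patient characteristics may be added where applicable; and the study is declared descriptive. These help in part. Subgroup tables do not repair the pooled estimate, and nothing requires puberty to be added. Follow-up ends when treatment stops, so many participants who finish growing will leave, but the 19-or-older band and the restart field show that non-growing participants are expected in the data.

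If the SDS does not exist in adults, it is simply missing and cannot move a mean. That holds for HVSDS with a reference that stops before 19. It does not hold for annual HV, nor for a reference with a very small SD.

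A reader might infer that mean HVSDS is driven by puberty artefact. The documents do not support that. They give no age or puberty mix, no frequency or length of pubertal delay, and no evidence of imbalance between arms; deviations of opposite sign can also partly offset. Individual deviations of several SDS should not be set directly against a small difference between group means. Nor is puberty timing the fault in adults, where the issue is the end of growth.

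**Conclusion.** The point holds in two parts of unequal strength.

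- **19 or older:** firm. It follows from the protocol's own age bands and its own account of when growth and treatment end. Velocity results in this band are uninterpretable, and unrestricted pooling lets adult values into the HV model.
- **9 to 18:** conditional on a chronological-age reference. HVSDS can then reflect puberty timing, and neither baseline-only puberty status nor Table 8-3 as listed corrects for it.

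The illustrated bias of -0.3 to +0.4 SDS requires an assumed 10-point imbalance and assumed artefacts of -3 or +4. It shows that the problem can exceed sampling error, not that it will. In the 0 to 2 and 3 to 8 bands the problem does not arise until puberty begins.

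**What to change.** 1. Remove Annual HV and HVSDS from the 19-or-older subgroup, and exclude participants aged 19 or older or at adult height from the HV and HVSDS models. Apply this by age at the growth interval, since participants age during follow-up.
2. Make the inferential HVSDS comparison only in growth intervals where the child is still prepubertal by recorded Tanner stage, testicular volume or menarche, or is below a sex-specific age fixed before analysis. Report HVSDS descriptively elsewhere.
3. Add time-updated puberty status to the annual HV and height SDS models for older children. Moving these children from HVSDS to annual HV alone would not remove the problem, because HV and height SDS are also sensitive to puberty timing.
4. Name the HVSDS reference and the ages it covers.

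The cost is protocol and SAP wording plus a filter on data already collected. Fewer intervals will contribute to HVSDS, and puberty data may be missing at some visits, so the rule for unclassifiable intervals should be set in advance.
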